Prospective participants who have not attained the legal age for consent (e.g. individuals under the age of 18 years), as determined by the age in their medical record, will be required to give written assent. Written parental permission will also be obtained for these individuals if the parent or guardian is present. Parental permission will be obtained from one parent, even if the other parent is alive, known, competent, reasonably available, and shares legal responsibility for the care and custody of the child. Only parents or legal guardians listed in the child's medical record will be able to provide permission. If the parent or guardian is not present, we will not contact them for the sole purpose of informed consent as doing so may violate the adolescents' right to private healthcare for certain sexual health services. We will instead present the participant with a consent form that provides enough information for the subject to make an informed decision. Given this study includes no more than minimal risk, we have applied for a Waiver of Parental Permission as permitted under permitted under 45 CFR 46.408(c) for those patients under 18 years of age who present alone for a visit for reproductive health visits.

21. Setting

Participants will be recruited from the CHOA Hughes Spalding Adolescent Medicine Practice and the Grady Health Teen Clinic Program. For patients visiting the clinics in person, recruitment procedures will take place either before the visit using the screening and recruitment phone call or in the waiting rooms of each clinic, while consent/assent and study procedures will take place in a private office. For patients visiting the clinics virtually (telemedicine) recruitment, consent, and study procedures will take place via Zoom videoconferencing (password-protected). Participants who agree to participate in the intervention in Aim 3 will attend a study visit at the Emory Children's Center Research Unit.

A CHOA community advisory board will be made available to us. The advisory board consists of local business, community and nonprofit leaders who are not only dedicated to community service, but also focused on the needs and well-being of children in their communities. Board members work as advocates and liaisons between the community and Children's.

22. Resources Available

The CHOA Hughes Spalding Adolescent Medicine Practice serves approximately 2000 adolescents ages 13-21 years of age annually for primary care wellness visits, as well as consultative behavioral/mental health and reproductive health visits. The Grady Teen

Clinic, a Title X funded family planning program, provides a dedicated teen-friendly space to both male and female adolescents ages 12 through 20 years and serves approximately 1500 adolescents annually. For the proposed study, we will need to

Page 18 of 20 IRB Form SOCIOB 08102020

recruit 60 AYA participants ages 13-21 years over the course of one year. We will devote three days out of the week to recruitment in order to reach our recruitment goal.

Both medical and psychological resources are available to participants who experience anticipated consequences of human research. **Security**, the project PI, is a provider at the CHOA Adolescent Medicine practice and can provide research-related care to patients at the recruitment site, as needed. Additionally, **Security**, the project Co-I, is a provider at the Grady Health Teen Program and can provide research-related care to patients at the recruitment site, as needed. The Adolescent Medicine practice also has two additional medical doctors, a nurse practitioner, and a licensed psychologist who will be made aware of the research study and will be able to provide care as needed to patients experiencing any stress identified via the research protocol. The Grady Health Teen Program has an additional medical doctor, a nurse practitioner, and a health educator/case manager who will be made aware of the research study and will be able to provide care as needed to patients experiencing any stress identified via the research study and will be able to provide care as needed to patients experiencing any stress identified via the research study and will be able to provide care as needed to patients experiencing any stress identified via the research protocol.

All persons assisting with the research will be adequately informed about the protocol, research procedures, and their duties and functions. Furthermore, all persons assisting with the research will receive appropriate CITI training

23. References

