women and the same 10 HCPs from Aim 1 to evaluate the #HerHeart tool's usability and feasibility. AYA participants will complete a brief initial survey consisting of demographic information and the Visual Analog Scale (VAS) and the #HerHeart tool in clinic. AYA participants will the rate the usability of the #HerHeart tool using the Website Analysis and Measurement Inventory (WAMMI), the likelihood they would recommend the app to their friends, and the likelihood of behavior change. AYA participants will then be offered the opportunity to continue into the 3-month intervention phase. We will document the reasons for declining as part of tracking feasibility. At the beginning of the intervention phase, participants will complete the Eating Disorder Diagnostic Scale (EDDS). Participants will then be texted 1 month and 2-months post-enrollment reminding them of any goals/areas of improvement indicated by their end assessment in the #HerHeart Tool. Three months post-enrollment, participants will attend the final study visit in the phlebotomy room on the second floor of CHOA Hughes Spalding. In this visit, AYA participants height, weight and blood pressure will be measured. Participants will also be asked to complete the #HerHeart tool again and the same online study scales collected at baseline (EDDS and VAS). They will also be asked to complete the Harvard Healthy Heart Score and evaluate the usability using the WAMMI. HCP participants will complete a survey consisting primarily of demographic information and the #HerHeart tool. HCP participants will then rate the usability of the tool using the WAMMI, the usefulness of the #HerHeart to their practice and the likelihood they would incorporate it into usual clinical care.

Data analysis will consist of descriptive statistics for the WAMMI and Likert scale surveys. Usability will be defined as >80% of AYA and HCP rating the application as above average on the WAMMI. Acceptability to HCP will be defined as a mean of 8 out of 10 Likert Scale items. Paired t-tests will be used to compare the baseline and 3-month data for the continuous scales (EDDS, VAS).

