Primary outcomes will include changes in overall #HerHeart risk score, composite dietary score, fruit and vegetable intake, red/processed meats intake, soda and sweetened beverages intake, nut consumption, cereal fiber consumption, alcohol consumption, nicotine use, and physical activity over a 3-month period. Secondary outcomes will include changes in BMI and systolic and diastolic blood pressure over a 3-month period. Exploratory outcomes will include usability of the HerHeart tool and Healthy Heart Score as assessed by the WAMMI, adolescents' likelihood of recommending the tool to friend, adolescents' self-reported likelihood of behavior change, adolescents' understanding of heart disease risk as measured by VAS, change in EDDS score, number of participants approached and participated, completion/dropout rate, HCP rated usefulness of HerHeart tool to the practice, and HCP rated likelihood of

incorporating HerHeart tool into practice.

All phases: The probability and magnitude of risks will be minimized by conducting study procedures in private settings, collecting data in REDCap, a secure web-based application designed exclusively to support data capture for research studies, and collaborating with the Georgia CTSA to ensure data security of the mobile app.

6. Data and Specimen Banking

Data from surveys/questionnaires, audio recordings, and interviews will be stored until the completion of data analysis and manuscript publication. Only approved study personnel listed on the protocol will have access to the data.

7. Sharing of Results with Participants

Personal Healthy Heart Score risk assessments will be shared with participants at each stage of the study. Participants will be encouraged to share their results with their primary care physicians, but results will not be directly shared with others.

8. Study Timelines

Individuals in Aim 1/Phase 1 will participate for ~one hour, one time. Individuals in Aim 2/Phase 2 will participate for up to two hours for each design session which will occur over 6 months. Aim 3/phase 3 will occur over 3 months. The total duration of the overall study is 15 months, which includes subject participation and data analysis.

9. Subject Population

Subjects will be recruited from the CHOA Hughes Spalding Adolescent Medicine Clinic and the Grady Teen Health Program. The following inclusion/exclusion criteria will be used for subject recruitment:

Inclusion Criteria (AYAs):

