- Patient at CHOA Hughes Spalding Adolescent Medicine Practice or the Grady Health System Teen Program
- Age 13-21 years
- Self-identifying as non-Hispanic Black or White race (inclusive of Hispanic ethnicity)
- Self-identifying as female
- Visit type is annual wellness/health check, behavioral/mental health, or reproductive/gynecological health
- Consistent access to a mobile device with internet capability

Exclusion Criteria (AYAs):

- Cognitive impairment limiting ability to complete study procedure
- Spoken and written language other than English

- Diagnosis of hypertension, diabetes, or hyperlipidemia requiring medications, or atherosclerotic cardiovascular disease
- Past or current diagnosis of a DSM-V eating disorder
- Diagnosis of schizophrenia, bipolar disorder, or psychiatric hospitalization in the past 12 months
- Pregnant at the time of the study.

Inclusion Criteria (HCPs):

- Clinical team member (physician or nurse practitioner, nurse, social worker, psychologist, health educator, medical assistant, dietitian) at the CHOA Hughes Spalding Adolescent Medicine Practice or the Grady Health System Teen Program
- Practicing at one of the study sites at least twice per month on average over the past year

Exclusion Criteria (HCPs)

- Member of the research study team

10. Vulnerable Populations

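### Phase 3 collects an eating-disorder scale at entry, but nothing supplied requires it to be scored or seen by a clinician before the month-1 and month-2 goal texts

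*Combined protocol and SAP*

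**What the plan says.** Section 5, Phase 3 sets the order of events. Participants complete #HerHeart in clinic, rate it, and are offered the 3-month intervention phase. For those who accept, "At the beginning of the intervention phase, participants will complete the Eating Disorder Diagnostic Scale (EDDS". Next, "Participants will then be texted 1 month and 2-months post-enrollment reminding them of any goals/areas of improvement". Then "Three months post-enrollment, participants will attend the final study visit in the phlebotomy room", when the EDDS is repeated.

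Two uses of the EDDS are given, both in Section 5. One is an analysis: "Paired t-tests will be used to compare the baseline and 3-month data for the continuous scales (EDDS, VAS". The other is a place among the exploratory outcomes: "change in EDDS score, number of participants approached and participated".

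The eating-disorder criterion in Section 9 excludes "Past or current diagnosis of a DSM-V eating disorder" and does not refer to the EDDS. Section 14 recognises that participants, once told their cardiovascular risk, may alter diet or exercise beyond what is advised.

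**The concern.** The protocol names a diet-and-exercise risk, excludes known eating disorders and collects a scale aimed at undiagnosed ones, yet uses that scale only as a group mean change. No score that prompts a look, person who looks, deadline or action is stated. The texts are not conditional on the result.

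At stake is the safety of an individual participant. Participants are 13 to 21 (Section 9), and some minors may enroll without parental permission (Sections 10 and 20). The texts point to areas for improvement drawn from a tool whose outcome domains include diet and physical activity. The research coordinator collects the data (Section 18) and has no part in participants' medical care (Section 20), so no clinician need see an answer when it is given.

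**Working it through.** The plan has no figure to reproduce. The check is whether any stated step puts an entry EDDS result in front of a clinician before the texts.

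**Timing (Section 5, Phase 3).** EDDS at month 0, texts at months 1 and 2, final visit at month 3. Both texts (2 of 2) come before the only dated follow-up visit. Section 21 also mentions a study visit for intervention participants at a different location, without a date. It may be the same visit.

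**Safeguards, one by one.**
- Section 9, exclusion: rests on a diagnosis, so it does not catch an undiagnosed case.
- Section 5, all phases: "The probability and magnitude of risks will be minimized by conducting study procedures in private settings", together with REDCap and app data security. None of these concerns the content of an answer.
- Section 16, REDCap checks: value range and skipped items, not clinical meaning.
- Section 17, participant safety monitoring: takes place at follow-up visits. The one with a date is after both texts.
- Section 17, adverse event monitoring and interim risk/benefit assessment: the latter extends to preliminary observations, which could include EDDS data, but the scale is not named and no time is set.
- Section 17, quarterly meeting of PI and biostatistician: covers data quality and safety events. EDDS results are not on the stated agenda.
- Section 13, withdrawal at PI discretion, and Section 22, clinic care as needed: both depend on someone already having noticed the problem.

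The paired t-test implies scoring at some point, but nothing sets when.

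**How far the quarterly meeting could help.** Assume meetings exactly 3 months apart, entry uniform over the cycle, and EDDS completion at enrollment. The wait from entry to the next meeting is then uniform on 0 to 3 months.
- Meeting before the month-1 text: 1/3 of participants. No meeting before it: 1 − 1/3 = 2/3.
- Meeting before the month-2 text: 2/3. No meeting before either text: 1 − 2/3 = 1/3.

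These are upper limits on what the meeting could catch before each text, since they suppose that entry EDDS results would be examined there.

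**Size.** Section 5 recruits 60 AYA participants for Phase 3, and only those who accept the offer reach the EDDS, so at most 60 are exposed. The documents give no opt-in rate, prevalence or EDDS cut-off, so the number with a concerning result cannot be derived.

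**The case against.** The strongest case against has four parts.

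**The step may exist elsewhere.** The screening survey (Section 12) and the Data and Safety Monitoring Plan still to be established (Section 17) were not supplied, and the parties who conduct ongoing review in Section 17 are blacked out. This stands as a limit. The readable list of reports does not mention the EDDS.

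**General oversight may catch cases.** A reader might infer that an entry result must stay unread for the whole three months. The documents do not support that. It is the worst case, because the quarterly meeting, the risk/benefit assessment or the undated Section 21 visit could intervene. None of them is required to do so before the texts.

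**The main exposure comes earlier.** Section 14 ties the risk to learning one's cardiovascular risk. #HerHeart is completed before the EDDS, and Section 7 shares personal risk results at each stage. Those who decline the intervention phase never complete the EDDS at all. This stands: review before the texts addresses only what the texts add.

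**The texts may be mild.** A reader might infer that the intervention promotes weight loss or calorie restriction. No such goal is stated, and the domains include nicotine, alcohol, nuts and cereal fiber. Still, diet and physical activity are also among them, and a reminder can concern either.

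The study also describes itself as minimal risk, excludes diagnosed cases and has clinicians on hand. That lowers the expected harm but does not supply the missing step.

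**Conclusion.** The concern holds as a safety gap in the procedure as written. A trial run exactly to the protocol can send both goal reminders to a participant whose entry EDDS is concerning and unread. The sponsor should correct it. Confidence is medium because of the documents not supplied.

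The size is bounded only from above, at 60 participants and two texts each. The quarterly-meeting fractions rest on the assumptions stated with them and are not figures from the plan.

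Two stronger readings are not supported. The first is that the plan breaches its own exclusion criterion: that criterion concerns a diagnosis, and enrolling someone undiagnosed does not contradict it. The second is that the EDDS comparison is invalid: the gap lies in what is done with individual results and gives no reason to fault the paired comparison.

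**What to change.** In Section 5, Phase 3, state that:
1. The EDDS is scored automatically in REDCap when completed at entry, and the protocol names in advance the result that triggers review. The documents give no cut-off, so the sponsor must choose and justify one.
2. The PI or Co-I reviews every triggering result before the month-1 text, which is held until the review is done.
3. If the reviewer judges that there is an eating-disorder concern, goal texts stop and the participant is referred to the clinic staff in Section 22. Otherwise she continues as planned.

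Do not use Section 13 withdrawal for this purpose. It ends data collection and removes the person from the final analysis, so those of most concern would lose the month-3 visit and its safety monitoring. Keep the month-3 visit, the repeat EDDS and all data already collected in the analysis. Report the numbers reviewed and stopped beside the EDDS change.

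Name a referral route for Grady, since the only psychologist listed in Section 22 is at the Adolescent Medicine practice. State how results are kept confidential for minors enrolled under the waiver.

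The cost is a little PI or Co-I time, an IRB amendment, and possibly a few participants who do not receive texts. No new scale, visit or participant time is needed. If the screening survey or monitoring plan already contains this step, a cross-reference in Section 5 is enough.

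### The secondary outcomes are 3-month changes in BMI and blood pressure, but measured height, weight and blood pressure are listed only at month 3, and no measured baseline is named.

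*Combined protocol and SAP*

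**What the plan says.** The Phase 3 outcome paragraph in Section 5 (Study Intervention / Design) reads: "Secondary outcomes will include changes in BMI and systolic and diastolic blood pressure over a 3-month period".

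The Phase 3 procedures in the same section run in order:

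- **Enrolment.** "AYA participants will complete a brief initial survey consisting of demographic information and the Visual Analog Scale (VAS) and the #HerHeart tool in clinic". Participants then rate usability (WAMMI) and give two likelihood ratings.
- **Start of the intervention phase**, for those who continue. "At the beginning of the intervention phase, participants will complete the Eating Disorder Diagnostic Scale (EDDS").
- **Months 1 and 2.** Text reminders only.
- **Month 3.** "participants will attend the final study visit in the phlebotomy room on the second floor of CHOA Hughes Spalding". Then: "In this visit, AYA participants height, weight and blood pressure will be measured". Participants also repeat the tool and complete "the same online study scales collected at baseline (EDDS and VAS"), and they complete and rate the Healthy Heart Score.

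The one before-and-after test in the analysis text is: "Paired t-tests will be used to compare the baseline and 3-month data for the continuous scales (EDDS, VAS").

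Section 21 (Setting) adds a visit without giving its timing or content: "Participants who agree to participate in the intervention in Aim 3 will attend a study visit at the Emory Children's Center Research Unit".

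**The concern.** A change needs a value at each end. The protocol commits to change in three physical measures but schedules the measuring once, at the end. A blood pressure that was not taken at entry cannot be taken later, so the gap has to be closed before participants enter the 3-month phase.

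If it is left open, staff may improvise: chart values for some, self-reported values for others, nothing for the rest. The reported change would then contain differences between methods as well as real change. Phase 3 describes no control group that could separate the two.

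**Working it through.** The plan gives no figure to reproduce, and its text gives no SD, so no effect in mmHg or kg/m² is claimed. The check sets the passages side by side.

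**1. What each outcome needs.** Change in SBP = SBP at month 3 − SBP at baseline, and likewise for DBP. Change in BMI = BMI at month 3 − BMI at baseline, where BMI = weight / height². Each needs 2 time points.

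**2. What Section 5 lists for Phase 3.**

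| Measure | Enrolment or start of intervention phase | Month 3 |
|---|---|---|
| #HerHeart tool | yes | yes, marked as a repeat |
| VAS | yes | yes, marked as a repeat |
| EDDS | yes | yes, marked as a repeat |
| Height, weight | not listed | measured |
| Blood pressure | not listed | measured |

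BMI, SBP and DBP therefore each have 1 named measured time point out of the 2 needed, which is 3 of 3 secondary outcomes. The text marks the tool, VAS and EDDS as repeats but says nothing of the kind about the physical measures.

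**3. Whether another section supplies the baseline.**

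- *Outcome table (Section 5).* It lists changes in SBP and DBP. It is broken in the supplied text, so whether it gave timing cannot be checked.
- *Clinic vitals.* Section 18 appears to limit access to participants' medical records to checking eligibility. A noun is missing from that sentence, so this is a reading. No section authorises taking vitals from the chart as outcome data.
- *Research-unit visit (Section 21).* It could be a baseline visit, or it could be the final visit at a different address from the one in Section 5. The text does not decide.
- *Monitoring (Section 17).* It describes all data as coming from self-report questionnaires or recorded interviews, so it names no physical measurement at any time.
- *The #HerHeart tool.* It is completed at both ends, but its items are not shown. It may ask for height and weight. Nothing in the text suggests that it supplies a measured blood pressure.

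**4. What a self-entered BMI baseline would do.** Let M₃ be measured BMI at month 3, S₀ the self-entered BMI at baseline, and M₀ the BMI that measurement at baseline would have given. Then

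M₃ − S₀ = (M₃ − M₀) + (M₀ − S₀).

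The first bracket is the change of interest and the second is the method difference. M₀ is never observed and there is no control group, so the brackets cannot be separated. A chart value from a different procedure raises the same problem.

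**5. Remote participants.** Section 5 places the Phase 3 baseline in clinic. Section 12, whose screening covers Aims 1 and 3, also offers a study visit by Zoom, and Section 21 has telemedicine patients complete study procedures by Zoom. Staff cannot take these measurements over video. The documents do not say how many participants this affects.

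**The case against.** The strongest reply is that a list can be incomplete. Defining the outcomes as changes itself implies two time points. Section 17's description of the data sources already fails to cover the month-3 measurements, so this protocol does not list everything. The Section 21 visit may be the baseline visit, and the defect would then be a missing cross-reference. The data-collection attachments are not shown.

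Much of this stands, and it limits the claim. A reader might infer that no baseline is taken, or that none of the three changes can be computed. The documents support neither. They show only that no measured baseline is named, and a BMI change from self-entered values cannot be excluded. The damaged Section 18 sentence also cannot firmly rule out chart values.

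The reply does not supply the missing instruction. Staff following Section 5 as written would measure blood pressure once, and an untimed visit with no listed measurements does not change that. Section 16's statement that all data are descriptive does not help either, because a descriptive mean change still needs both values.

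**Conclusion.** The point holds in a limited form and should be fixed. All 3 secondary outcomes lack a named measured baseline. For SBP and DBP, the procedures as listed yield no change at all. For BMI, they yield at best a comparison of self-entered with measured values, and only if the tool collects height and weight.

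This rests on the supplied text alone and on two assumptions: that the unseen attachments do not schedule a baseline, and that the Section 21 visit is not one. If either fails, a sentence stating when, where and how the baseline is taken would settle it.

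It would be wrong to infer that Phase 3 as a whole is compromised. Section 4 sets its endpoint as usability and recruitment feasibility, and neither that endpoint nor the usability and acceptability criteria in Section 5 use these measurements.

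**What to change.** 1. In the Phase 3 procedures of Section 5, add measured height, weight and blood pressure at entry to the 3-month phase for every participant who continues, by the same procedure as at month 3.
2. Reconcile Sections 5 and 21: state whether the visit at the Emory Children's Center Research Unit is the baseline visit or the final visit that Section 5 places at CHOA Hughes Spalding.
3. Where an in-person baseline is not feasible, for example after Zoom enrolment, explicitly authorise abstraction of enrolment-day clinic vitals where they exist. Amend the Section 18 access statement to match, and state the method difference as a limitation. Otherwise count the participant as missing for these outcomes. The same applies to anyone already enrolled without measured values; the documents do not give enrolment status.
4. Report change only in participants with both values, and give the number of pairs. The paired tests now planned name only EDDS and VAS, so this analysis needs its own sentence.

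The cost is a few minutes per participant (assumed), measuring equipment wherever the baseline takes place, and some missing pairs among remote participants.

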the study procedures as described in Section 6. Consent and study procedures will only occur in the context of a study visit, and not via initial phone screening and recruitment.

To assist with recruitment efforts, a recruitment flyer containing information about the study (eligibility requirements, study procedures, time commitment, etc.) will be distributed in the CHOA Adolescent Medicine practice. The flyers will be distributed to eligible patients who may not have time to begin the study procedures due to normal clinic flow (i.e., patient gets called back to exam room before we can consent them and begin the study).

Compensation for participants will be as follows:

- Aim 1: AYA and HCP subjects will receive a \$25 gift card.
- Aim 2: AYA subjects will receive a \$50 gift card.
- Aim 3: AYA will receive up to \$60 and HCPs will receive \$25

13. Withdrawal of Participants

Participants will be told that they can drop out of the study at any time during the study. Participants who become pregnant or become cognitively impaired throughout study duration will be withdrawn from the study without their consent. Furthermore, participants who become otherwise unable to participate in the research procedures due to health-related concerns will be withdrawn from the research without their consent at the discretion of the PI. Data collection will cease for participants who withdraw from the research and these individuals will not be included in the final data analysis.

14. Risks to Participants

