This proposed study involves no more than minimal risk. Completion of the Healthy Heart risk assessment tool in its current form includes the risk that AYA participants disclose heavy alcohol or tobacco use. Participants may find learning about their cardiovascular risk distressing. After learning about their cardiovascular risk, participants may make changes to their exercise or dietary habits outside of what is recommended in the behavioral intervention or would be recommended by their HCP. Participation in the interviews also carries the risk of AYA's self-disclosure of health information. All efforts will be made to remind participants not to provide identifying information during the interviews. Breach of confidentiality is a risk for both AYA and HCP participants. To ensure participant confidentiality, study identification numbers will be assigned to each participant and used throughout the duration of the study when referring to subjects. The codes that link the name of the participant and the study identification number will be kept confidential by the PI in a secured cabinet. Only the authorized study team with appropriate training will have access to the data.

The direct benefit to AYA participants in the survey and interviews in each aim is gaining information about their health. The direct benefits to HCP in Aim 1 includes learning about new tools or methods that can potentially be used to increase CVD awareness in patients. Overall this study has the potential to inform prevention practices applicable to millions of young women living in the United States and to possibly lower the burden of cardiovascular disease among women.

Though not considered a benefit, subjects will be compensated for participation in this study. In Aim 1, AYA and HCP subjects will receive a \$25 gift card for completing surveys and interviews. In Aim 2, AYA participants will receive a \$50 gift card for participating in the design sessions. In Aim 3, AYA participants will receive \$25 for completing the usability assessment and up to \$35 for completing the intervention phase; HCPs will receive \$25 for completing the usability assessment.

16. Data Analysis, Management and Confidentiality

The main aim of the proposed study is to adapt the Healthy Heart Score tool based on participant feedback. As such, all data will be descriptive only.

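### Sections 5 and 16 disagree on whether EDDS and VAS are tested, and a comparison of EDDS means alone can miss worsening in a few participants

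*Combined protocol and SAP*

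**What the plan says.** Section 5 (Procedures Involved, Phase 3) gives descriptive summaries to the WAMMI and the Likert ratings, then adds: "Paired t-tests will be used to compare the baseline and 3-month data for the continuous scales (EDDS, VAS"). Its outcome list places both scales among the exploratory outcomes, worded as "understanding of heart disease risk as measured by VAS, change in EDDS score". EDDS is completed at the start of the optional 3-month phase and again at the 3-month visit. No cut-off, scoring rule or count of participants is given for it.

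Section 16 reads: "The main aim of the proposed study is to adapt the Healthy Heart Score tool based on participant feedback". The next sentence is: "As such, all data will be descriptive only".

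Three other sections bear on EDDS:

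- Section 9 excludes anyone with "Past or current diagnosis of a DSM-V eating disorder".
- Section 14 warns that "participants may make changes to their exercise or dietary habits outside of what is recommended in the behavioral intervention".
- Section 13 provides that "participants who become otherwise unable to participate in the research procedures due to health-related concerns will be withdrawn" at the investigator's discretion. It also says: "Data collection will cease for participants who withdraw from the research and these individuals will not be included in the final data analysis".

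Section 17 sets up tracking of drop-outs, adverse-event monitoring and safety monitoring at follow-up visits. It does not mention EDDS.

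**The concern.** There are two separate issues.

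The first is a conflict of instructions. An analyst following Section 16 would run no test on EDDS or VAS, and one following Section 5 would run paired t-tests on both. Section 16 is the section headed as data analysis, and its sentence is not limited to Aims 1 and 2.

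The second is what the EDDS analysis can show. Participants are aged 13 to 21 and are reminded by text of goals from a tool that covers diet and activity. The protocol itself recognises that some may go further than advised. If that happens, it is likely to affect a few participants rather than shift the whole group. A mean averages those few with everyone else, so the report could show no change while several participants had newly met the scale's criteria. Anyone who worsens and withdraws contributes no EDDS change at all.

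**Working it through.** **The two instructions side by side.** Section 5 names a test for two scales. Section 16 says everything is descriptive. A paired t-test is not a descriptive summary, so both cannot be followed as written. Section 16 derives its sentence from the adaptation aim, and the more specific Phase 3 text would probably govern, but the document does not say so.

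**Inputs for the EDDS check.** The documents give no EDDS standard deviation, cut-off, significance level or expected number of completers, so there is no plan figure to reproduce. The only anchor is the 60 young women recruited to Phase 3, an upper bound on the number of pairs because the 3-month phase is optional. Everything else is assumed: n = 45 pairs (also 30 and 60), normally distributed change with SD 1, k participants worsening by s SD of change, the rest changing by m on average (m = 0 unless stated), and a two-sided 5% test.

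**Mean shift.** Expected mean change = [k·s + (n − k)·m] / n. With n = 45, k = 3, s = 2, m = 0, this is 6/45 = 0.13 SD. For comparison, 80% power needs a mean shift of 0.37 SD at n = 60 and 0.53 SD at n = 30.

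**Chance of a significant result in the direction of worsening** (simulation; 2.5% if nobody worsens):

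| Pairs | Worsening | Shift (SD) | Others' mean change | Mean change (SD) | Significant worsening |
|---|---|---|---|---|---|
| 45 | 3 | 2 | 0 | 0.13 | 9.5% |
| 60 | 3 | 2 | 0 | 0.10 | 8% |
| 30 | 3 | 2 | 0 | 0.20 | 11% |
| 60 | 3 | 2 | −0.1 | 0.005 | 2% |
| 30 | 3 | 2 | −0.1 | 0.11 | 4% |
| 60 | 5 | 3 | 0 | 0.25 | 26% |
| 60 | 5 | 3 | −0.1 | 0.16 | 8% |

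In the fourth row, (3 × 2 − 57 × 0.1)/60 = 0.3/60 = 0.005: a slight improvement in the other 57 cancels the three who worsen.

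**Effect of Section 13.** Start from 45 pairs with 3 worsening by 2 SD. If one of the three leaves, 44 pairs remain with 2 worsening: mean change 4/44 = 0.09 SD, significant worsening 6.2%. If two leave, 43 pairs remain with 1 worsening: 2/43 = 0.05 SD, 4.0%.

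**What a count would show.** 3/45 = 6.7%, exact (Clopper-Pearson) 95% CI 1.4% to 18.3%. 2/44 = 4.5%, CI 0.6% to 15.5%. With no cases, the upper limit is 11.6%, 7.9% or 6.0% at n = 30, 45 or 60. If the true rate of newly meeting criteria were 5% (assumed), the chance of at least one case is 1 − 0.95^n = 79%, 90% or 95% at those n. The count answers a different question from the test, so these are not competing powers.

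**The case against.** The strongest reply is that the conflict is editorial. Both scales are exploratory, nothing else in the design depends on them, and one clause settles it. That stands, and it is why this half is minor.

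A second reply is that the documents never say why EDDS is collected. They treat it as a continuous scale, so a safety purpose is the reader's inference. A blanket promise of description also does not forbid describing individual scores. This stands in part: Sections 9 and 14 make individual worsening relevant but do not make EDDS a declared safety measure. What is missing is a stated summary, and adding one is an improvement rather than the repair of an error.

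Three stronger readings are tempting, and the documents do not support them:

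- *Participants who leave go unseen.* Completion and drop-out are listed outcomes, and Section 17 provides for adverse-event monitoring and quarterly review. Only their EDDS change is lost. Nothing says that a worse EDDS score leads to withdrawal.
- *After such losses the test does no better than chance.* That compares a two-sided rejection rate with 5%. In the direction of worsening, the 43-pair case gives 4.0% against 2.5%, which is low but above chance.
- *The 10 primary and 3 secondary changes are wrongly left without a statistic.* The descriptive statement in Section 16 covers them. The detail is thin, but there is no contradiction to correct there.

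**Conclusion.** The point holds in two modest parts. First, Sections 5 and 16 contradict each other on EDDS and VAS and must be reconciled. The consequence is confined to two exploratory outcomes. Second, the only stated EDDS analysis would usually miss worsening in a few participants: about 9.5% detection with 3 of 45 worsening by 2 SD, and between 2% and 26% over the settings tabulated.

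The direction of this result follows from averaging. Its size rests on assumed values for the number of pairs, the number worsening, the size of shift and the normal distribution of change. Nothing here shows that harm is expected, or that the study's usability and feasibility conclusions are affected.

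**What to change.** 1. **Reconcile the sections.** Either limit the Section 16 sentence to the adaptation work in Aims 1 and 2, or name the EDDS and VAS paired comparisons as its exception. Report those two mean changes with a 95% CI, labelled exploratory. The other Phase 3 outcomes need no change on this account.

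2. **Add two EDDS counts beside the mean change.** The first is the number newly meeting the scale's scoring criteria at 3 months, among participants who did not meet them at baseline and have both assessments, with an exact 95% CI. The scoring rule must be named before analysis, since the documents give none. The second is the number with a baseline EDDS but no 3-month EDDS, with reasons where known. The Section 13 analysis set stays as it is.

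**Cost.** A few sentences. EDDS and VAS are already collected at both times, and drop-outs are already tracked. The interval on the count will be wide, and the report should say that, with no control arm, worsening cannot be attributed to the intervention. The second count shows how much EDDS information is missing but does not recover it.
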